3. ANALYSIS OF THE CNS ENDPOINTS

Additional details on the CNS endpoints are provided in this section.

3.1. Secondary CNS endpoint

The secondary CNS endpoint is time to intervention for symptomatic CNS disease. This is defined as the time from the date of randomization to the first date of an intervention for symptomatic metastatic CNS disease. Interventions include medications to control signs or symptoms caused by the CNS metastases (ie, high dose steroids in case of cranial hypertension), CNS radiotherapy, CNS surgery and cancer treatment specific for CNS metastases.

3.2. Progressive CNS Endpoint

The alternative CNS endpoint is time to progressive CNS lesions. This is defined as the time interval from the date of randomization until the first date on which a scheduled or unscheduled tumor assessment documents the appearance of newly diagnosed or progressive CNS lesions, per RECIST v1.1. For subjects that have CNS lesions as target lesions, the sum of the longest diameter (SLD) of CNS lesions only will be calculated at each tumor assessment and if the change from the nadir is greater than 20% this will be considered progressive CNS disease. If the subject has nontarget CNS lesions progressive CNS disease will be considered if any of the nontarget CNS lesions have a status of unequivocal progression. If the subject had a newly diagnosed CNS lesion post-baseline this will be considered progression as well.

3.3. Statistical Analysis

3.3.1. Sensitivity analysis for the secondary CNS endpoint

1. The Kaplan Meier method, stratified log-rank test, and Cox proportional hazard model will be performed without considering competing events. A Kaplan-Meier curve with the results of the Cox model will summarize this analysis.
2. An analysis only looking at time to first dose of radiation for symptomatic CNS will be performed. Subjects that do not have a radiation intervention for symptomatic metastatic CNS and do not die will be censored at the last date known alive on or prior to the data cutoff. Deaths or other treatments for symptomatic CNS are treated as competing events.
3. A subgroup analysis only including subjects with a prior or current history of CNS metastases at the time of randomization will be done for the secondary CNS endpoint. A prior history will be defined as location of disease in the brain at screening, prior radiation of the brain, and prior surgery in the brain.

3.3.2. Time to progressive CNS disease

The time to progressive central nervous system (CNS) lesions will be analyzed using the centrally reviewed tumor assessments as well as the investigator tumor assessments.

Time to progressive CNS lesions is defined as the time interval from the date of randomization until the first date on which a scheduled or unscheduled visit documents the appearance of newly

diagnosed or progressive CNS lesions, per RECIST v1.1. Table 4 lists the CNS locations for the derivation of CNS progression based on the central or local tumor assessment data. All progressive CNS events will be counted regardless of their timing with regards to progression at other sites. Competing events include progression at other sites and deaths prior to the observance of progressive CNS. If there is no evidence of CNS progression or a competing event, the subject will be censored at the last assessable tumor evaluation on study or prior to new anti-cancer therapy, if applicable. Gray's test (Gray, 1988) stratified for factors used in the randomization will assess the equality of cumulative incidence functions between the treatment arms. The cause specific hazard ratio and p-value will also be performed. Additionally, the Kaplan Meier method, stratified log-rank test, and stratified Cox proportional hazard model will be performed without considering competing events. For this analysis subjects will be censored at the time of PD at a site other than CNS or at their last viable tumor assessment for subjects that did not have a PD. For these CNS endpoints the same censoring rules as those specific in the main SAP for the PFS analysis will be applied. Events, CNS events or any competing events, after the start of a new anti-cancer therapy or after 2 missed assessments will be censored and not considered as events.

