Complete Response (CR): Disappearance of all target lesions. Any pathological lymph nodes (whether target or non-target) must have reduction in short axis to <10 mm.

Partial Response (PR): At least a 30% decrease in the sum of diameters of target lesions, taking as reference the baseline sum diameters.

Progressive Disease (PD): At least a 20% increase in the sum of diameters of target lesions, taking as reference the smallest sum on study (this includes the baseline sum if that is the smallest on study). In addition to the relative increase of 20%, the sum must also demonstrate an absolute increase of at least 5 mm. (Note: the appearance of one or more new lesions is also considered progression).

Stable Disease (SD): Neither sufficient shrinkage to qualify for PR nor sufficient increase to qualify for PD, taking as reference the smallest sum diameters while on study.

Evaluation of non-target lesions

This section provides the definitions of the criteria used to determine the tumor response for the group of non-target lesions.

While some non-target lesions may actually be measurable, they need not be measured and instead should be assessed only qualitatively at the time points specified in the protocol.

Complete Response (CR): Disappearance of all non-target lesions and normalization of tumor marker level. All lymph nodes must be non-pathological in size (<10 mm short axis).

Non-CR/Non-PD: Persistence of one or more non-target lesion(s) and/or maintenance of tumor marker level above the normal limits.

Progressive Disease (PD): Unequivocal progression of existing non-target lesions. (Note: the appearance of one or more new lesions is also considered progression).

Target Lesions	Non-target Lesions	New Lesions	Overall Response
CR	CR	No	CR
CR	Non-CR/non-PD	No	PR
CR	Not evaluated	No	PR
PR	Non-PD or not all evaluated	No	PR
SD	Non-PD or not all evaluated	No	SD
Not all evaluated	Non-PD	No	NE
PD	Any	Yes or No	PD
Any	PD	Yes or No	PD
Any	Any	Yes	PD

Abbreviations: CR: complete response; NE: not evaluated; PD: progressive disease; PR: partial response; SD: stable disease.

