Progressive Disease (PD): At least a 20% increase in the sum of diameters of target lesions, taking as reference the smallest sum on study (this includes the Baseline sum if that is the smallest on study). In addition to the relative increase of 20%, the sum must also demonstrate an absolute increase of at least 5 mm. PD can also be determined if there is unequivocal progression of existing non-target lesions. (Note: the appearance of one or more new lesions is also considered progression).

Stable Disease (SD): Neither, sufficient shrinkage to qualify for PR, nor sufficient increase to qualify for PD, taking as reference the smallest sum diameters while on study.

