Cumulative incidence of time to intervention for symptomatic CNS is defined as time from randomization to the start of therapy for symptomatic CNS. Competing event are deaths prior to intervention for symptomatic CNS. Gray's test (Gray, 1988) stratified for factors used in the randomization will assess the equality of cumulative incidence functions between the treatment arms. Additionally, the Kaplan Meier method, stratified log-rank test, and Cox proportional hazard model will be performed without considering competing events.

As a sensitivity analysis to the secondary CNS endpoint, the time to progressive central nervous system (CNS) lesions will be analyzed using the centrally reviewed tumor assessments as well as the investigator tumor assessments. Time to progressive CNS lesions is defined as the time interval from the date of randomization until the first date on which a scheduled or unscheduled visit documents the appearance of newly diagnosed or progressive CNS lesions, per RECIST v1.1. If there is no evidence of CNS progression, the subject will be censored at the last assessable evaluation on study or prior to new anti-cancer therapy, if applicable. Competing events include progression at other sites and deaths prior to progressive CNS. Gray's test (Gray, 1988) stratified for factors used in the randomization will assess the equality of cumulative incidence functions between the treatment arms. Additionally, the Kaplan Meier method, stratified log-rank test, and Cox proportional hazard model will be performed without considering competing events.

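### Time to progressive CNS lesions (supplemental SAP 3.2 and 3.3.2): CNS progression after progression elsewhere has two incompatible statuses, and the target-lesion rule drops RECIST's 5 mm increase

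*SAP*

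**What the plan says.** **Timing rule.** Supplemental SAP 3.3.2 first states: "All progressive CNS events will be counted regardless of their timing with regards to progression at other sites". The next sentence reads: "Competing events include progression at other sites and deaths prior to the observance of progressive CNS". Gray's test and a cause-specific hazard ratio follow. A Kaplan-Meier, log-rank and Cox version that ignores competing events has its own rule: "For this analysis subjects will be censored at the time of PD at a site other than CNS". A closing limit applies throughout: "Events, CNS events or any competing events, after the start of a new anti-cancer therapy or after 2 missed assessments will be censored".

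Main SAP 8.3.2 defines the same analysis with the competing-event rule alone: "Competing events include progression at other sites and deaths prior to progressive CNS". It has no sentence that counts CNS progression whatever its order.

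**Target-lesion rule.** Supplemental SAP 3.2 cites RECIST v1.1, takes the sum of the CNS target lesions only, and then says: "if the change from the nadir is greater than 20% this will be considered progressive CNS disease". The main SAP's definition of progressive disease in section 8.2 adds to the 20% that "the sum must also demonstrate an absolute increase of at least 5 mm". Protocol Appendix 7 says the same: "In addition to the relative increase of 20%, the sum must also demonstrate an absolute increase of at least 5 mm". Both put the relative threshold at 20% or more.

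**Status.** Main SAP 8.3.2 calls this a sensitivity analysis for the secondary CNS endpoint. Section 8.3 leaves it out of the testing sequence, so it carries no alpha.

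**The concern.** A competing-risks analysis needs one first event, with one date, for each patient. Adjacent sentences in 3.3.2 give two different ones to any patient whose disease progresses outside the CNS first and in the CNS later. The choice between them would be left to programming, although the plan exists to settle it beforehand.

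In 3.2 the written-out rule is looser than the criteria it cites. A programmer who codes it as written would call CNS progression on growth that RECIST v1.1 classes as stable.

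This analysis is the imaging-based check on time to CNS intervention. It is run on both central and investigator readings and feeds four planned tables and four planned figures in the supplement. An ambiguous event definition weakens that check.

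**Working it through.** The plan gives no event count, power or rate for this analysis, so there is no stated figure to reproduce. The check compares the texts and works out the cut-offs.

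**1. Timing rule: one patient followed through 3.3.2.** Assume non-CNS progression at week 12, CNS progression at week 18, no new therapy and no two missed assessments.

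| Rule in supplemental SAP 3.3.2 | Status | Date |
|---|---|---|
| First sentence (count every CNS progression) | CNS event | Week 18 |
| Second sentence (earlier progression elsewhere competes) | Competing event | Week 12 |
| Kaplan-Meier/Cox version | Censored | Week 12 |

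The first two rows govern the same analyses, Gray's test and the cause-specific hazard ratio, and cannot both hold. The third row agrees with the second, because censoring at non-CNS progression is the usual counterpart of treating it as a competing event. It disagrees with the first. If the first sentence is followed, the competing-risks analyses and the Kaplan-Meier/Cox version therefore count different CNS events.

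**2. How many such patients can arise.** Three provisions limit the number:
- Scheduled scans stop at documented progression (protocol Appendix 1, footnotes i and q).
- Events after new anti-cancer therapy are not counted.
- Events after two missed assessments are not counted. On the 6-week grid this leaves a window of about 2 × 6 = 12 weeks after the last scan.

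Unscheduled assessments do count, so the number need not be zero. It cannot be derived from the documents.

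**3. Target-lesion rule.** Let *n* be the nadir sum of CNS target lesions in mm.
- Supplement: progression if the sum exceeds 1.2*n*.
- RECIST v1.1 as given in main SAP 8.2 and Appendix 7: progression if the sum is at least max(1.2*n*, *n* + 5).
- The two cut-offs meet where 1.2*n* = *n* + 5, so *n* = 5/0.20 = 25 mm.

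| Nadir sum (mm) | Supplement: above | RECIST: at or above | RECIST growth needed |
|---|---|---|---|
| 5 | 6 | 10 | 100% |
| 10 | 12 | 15 | 50% |
| 15 | 18 | 20 | 33% |
| 20 | 24 | 25 | 25% |
| 25 | 30 | 30 | 20% |

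An increase from 10 to 12.5 mm (25%, 2.5 mm) is progression only under the supplement. From 25 mm upward the rules differ only at exactly 20% growth: 25 to 30 mm is progression under RECIST but not under the supplement.

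**4. Are sums below 25 mm plausible?** Appendix 7 allows at most two target lesions per organ and sets the minimum measurable size on CT at 10 mm. If the CNS is counted as one organ (an assumption; the documents do not say), two lesions sum to less than 25 mm whenever their mean is below 25/2 = 12.5 mm. A nadir after shrinkage can be smaller still.

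**The case against.** On timing, the best defence is a hierarchical reading: CNS progression is the event whenever it is seen, and non-CNS progression competes only in patients who never progress in the CNS. The first sentence is an addition to the main SAP's text and may be deliberate. The supplement does not state this hierarchy, however. It would also classify a patient at week 12 by what happens later, and it would still disagree with the Kaplan-Meier/Cox censoring. It is fair to say that the Kaplan-Meier/Cox rule is not a third conflicting reading, since it matches the second sentence.

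A second argument is that deleting the sentence is only one way out, because making death the sole competing event would also remove the conflict. That is true. Deletion is the better choice because it restores main SAP 8.3.2, matches the existing Kaplan-Meier/Cox censoring and fits a scan schedule that ends at progression.

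On the 5 mm point, the reference to RECIST v1.1 could be read as importing the missing condition, with the 20% as shorthand. An explicit algorithm is what will be coded, though, and a general citation does not override it. The difference between more than 20% and at least 20% is trivial.

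The argument about reach largely stands. Symptomatic or unstable brain metastases are excluded (protocol 5.2), and scheduled follow-up imaging in Appendix 1 covers chest, abdomen and pelvis. CNS progression can also be called on new or non-target lesions, which the 5 mm rule does not affect.

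**Conclusion.** Both defects hold. As written, supplemental SAP 3.3.2 gives a patient with non-CNS progression followed by CNS progression two incompatible statuses in the competing-risks analyses. Section 3.2 departs from the RECIST rule it cites for every CNS nadir sum below 25 mm, with the gap in cut-offs widening as the sum shrinks (3 mm at a nadir of 10 mm, 1 mm at 20 mm).

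The reach is limited. The analysis has no alpha, and PFS, OS and the formally tested time to CNS intervention do not depend on it. The number of patients affected is unknown and probably small. The 25 mm threshold is plain arithmetic; only the remark on how often two lesions fall below it assumes that the CNS counts as one organ. The correction should be made because the rules as written can misclassify patients and the change is nearly free.

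**What to change.** - **Supplemental SAP 3.3.2:** delete the sentence that counts CNS progression regardless of its order relative to other sites. Keep first non-CNS progression and death as competing events, as in main SAP 8.3.2. Gray's test, the cause-specific hazard ratio and the Kaplan-Meier/Cox version then treat non-CNS progression consistently.
- **Supplemental SAP 3.2:** define target-lesion CNS progression as an increase from nadir of at least 20% and at least 5 mm in the sum of CNS target lesions. The CNS-only sum can stay.
- **If either departure was intended:** say so and carry it through. Counting later CNS progression would mean that death is the only competing event and that the Kaplan-Meier/Cox version no longer censors at non-CNS progression. Dropping the 5 mm condition would mean declaring that the rule is not RECIST v1.1.

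The cost is two sentences and no new data. CNS progressions first seen after non-CNS progression become competing events, and growth of less than 5 mm in small CNS target lesions is no longer called progression.

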4. SENSITIVITY ANALYSIS FOR OVERALL RESPONSE RATE

The SAP indicates that only subjects with measurable disease at baseline will be used in the calculation of Overall Response Rate. As a sensitivity analysis, all subjects will be included in the calculation. For subjects that only have non-target lesions at baseline, they can only be considered a responder if they achieve CR in all non-target lesions.

5. PROGNOSTIC VARIABLES OF INTEREST

The following prognostic variables will be investigated for the primary endpoints of PFS and OS.

1. Previous HER2 directed therapies
 - a. Trastuzumab only
 - b. TDM-1 only
 - c. Trastuzumab and Pertuzumab
 - d. Trastuzumab and T-DM1
 - e. Trastuzumab and Pertuzumab and T-DM1
2. De Novo and non De Novo disease at diagnosis

De novo disease at diagnosis is defined as having M stage of M1 or if the date of initial diagnosis is equal to or within 45 days of the date of first presentation with distant metastatic disease.

6. ADDITIONAL EXPLORATORY ANALYSIS

The following exploratory analyses for PFS will be performed.

6.1. Time to RECIST defined PFS or clinical progression

For this analysis all the definitions stated in the main SAP apply but the definition of PD is expanded to include subjects that ended treatment for clinical progression and did not experience PD per RECIST.

6.2. Time to treatment failure

Time to treatment failure is defined as the time from randomization to treatment discontinuation for any reason. For those subjects that are still on treatment at the time of the analysis, they will be censored on the data cut-off date.

Table 2: List of Planned Tables

Grouping	Title
HOA analysis	
Descriptive HOA	Summary of scale scores and change from baseline at each cycle (26 tables)
HOA Mixed model	Summary of model results for each subscale (26 tables)
HOA reduced mixed model	Summary of estimated means at each cycle for each subscale (26 tables)
Response analysis	Summary of response by subscale (7 tables)
AUC Analysis	Summary of ANCOVA model results (1 table)
Completion analysis	Summary of overall completion (1 table)
	Summary of completion by visit (1 table)
CNS Analysis	
Time to intervention for symptomatic CNS	Summary of time to intervention for symptomatic CNS
CNS disease progression	Summary of CNS Progression-Free Survival – Central Assessment
	Summary of CNS Progression-Free Survival – Local Assessment
CNS disease progression – no competing events	Summary of CNS Progression-Free Survival – Central Assessment
	Summary of CNS Progression-Free Survival – Local Assessment
PFS sensitivity analysis	Summary of Progression-free survival including EOT for clinical progression.
Sensitivity for ORR	Summary of ORR and CBR (ITT Population)
Time to treatment failure	Summary of time to Treatment Failure

Table 3: List of Planned Figures

Grouping	Title
QOL analysis	
Descriptive QOL	Figure of scale scores at each cycle (26 figures)
	Figure of change from baseline in each scale (26 figures)
Estimated means from mixed model	Mixed Model Results by Cycle (Change from Baseline) (26 figures)
Time to deterioration	KM curve by treatment group (7 figures)
CNS Analysis	
Time to intervention for symptomatic CNS	Cumulative hazard curves
	KM curve for no competing events
CNS disease progression – with competing risks	Cumulative hazard curve for CNS Progression-Free Survival – Central Assessment
	Cumulative hazard curve for CNS Progression-Free Survival – Local Assessment
CNS disease progression – no competing events	KM curve for CNS Progression-Free Survival – Central Assessment
	KM curve of CNS Progression-Free Survival – Local Assessment
Other	
KM of time to treatment discontinuation	KM curve of time to treatment discontinuation
Sensitivity for PFS	KM curve of time to PFS including clinical progression
Forest Plot for prognostic factors – PFS	Forest plot including prior treatments and DeNovo Disease for Central PFS
Forest Plot for prognostic factors – PFS	Forest plot including prior treatments and DeNovo Disease for Local PFS
Forest Plot for prognostic factors – OS	Forest plot including prior treatments and DeNovo Disease for OS

Table 4: List of CNS locations

	Bioclinica (Central review)	INFORM (Local review)
CNS Locations	Basal Ganglia Brainstem Caudate Cerebellum CNS (Brain) Corpus Callosum Dural Epidural Falx Fourth Ventricle Frontal Lobe Frontoparietal Hippocampus Lateral Ventricle Leptomeningeal Occipital Lobe Parietal Lobe Parietoccipital Spinal Cord Subdural Temporal Lobe Temporaloccipital Temporalparietal Thalamus Third Ventricle	Brain CNS Retina
